Proposal: Temporal variation in exhaled volatile organic compounds in response to therapeutic intervention in esophageal cancer patients

Principal investigator:

[name] FACS FRCS (c) FRCSE (Hon) FRCSE (Hon)
Head Of Thoracic Surgery and Thoracic Oncology
Director Digestive Disease Institute Esophageal Center of Excellence
President Ryan Hill Research Foundation
Virginia Mason Medical Center
[name]
[name]
[contact]
Email: [contact]

Co-investigator:

[name] [name]
Professor of Surgical Sciences
Head of Division of Surgery
Department of Surgery and Cancer,
Imperial College London,
St Mary's Hospital,
[name]
[contact]
E-mail: [contact]

**APPROVED
06/29/2020
BRI IRB**

SPECIFIC AIMS

Hypothesis: we hypothesize that cancer-associated Volatile Organic Compounds (VOCs) will vary significantly following therapeutic intervention in patients with esophageal cancer (EC) and that variation will predict treatment response.

Primary aim: to determine longitudinal variation in exhaled VOC concentrations during intended curative therapy for EC cancer.

Secondary aims:

- i. To validate the previously published model for a exhaled VOC breath test of EC cancer
- ii. To correlate the exhaled VOCs of EC cancer patients to important clinical parameters
- iii. To determine the relationship between exhaled VOCs and response to neoadjuvant chemoradiotherapy
- iv. To study changes in exhaled VOCs following tumor resection and their association with disease recurrence.
- v. To correlate the exhaled and urinary VOC concentrations in EC cancer patients
- vi. To longitudinal variation in the upper gastrointestinal microbiome and its relationship to exhaled and urinary VOC concentrations.

STUDY OUTCOMES

Primary outcome

- i. Confirmation of exhaled and urinary VOC biomarkers of EC cancer

Secondary outcomes

- i. Verification of changes in VOC concentrations that occur in response to therapeutic intervention
- ii. Refine diagnostic model for the detection and monitoring of EC cancer through analysis of exhaled VOCs
- iii. Linkage of longitudinal VOC data to predominant upper gastrointestinal bacterial species
- iv. Patient acceptability of breath test

BACKGROUND AND SIGNIFICANCE

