The analysis of VOCs excreted within exhaled breath is a particularly attractive diagnostic prospective as it offers a potentially non-invasive window on to normal human physiology and disease states within the body. Examples of the analysis of exhaled VOCs within clinical practice include breathalyzer devices for ethanol detection, ¹³C urea breath testing for *H. pylori*, exhaled Nitric Oxide in asthma and Hydrogen/Methane testing for small bowel bacteria overgrowth (4-7). There is now an appreciation that increased production of certain VOCs may be associated with cancer. In a recent literature review, we identified 63 publications presenting data for target VOC analysis in 12 distinct cancer subtypes. Pooled analysis of these studies revealed a combined sensitivity and specificity of 79% (95% CI 77%-81%) and 89% (95% CI 88%-90%) respectively for a 'cancer breath test'. This review included six publications concerning the VOC-based breath tests for the diagnosis of EC cancers (8-13). VOCs released from the urine of EC cancer patients has also been shown to contain a unique profile, although no study has directly compared this to breath signatures (14).

Our approach to addressing this clinical challenge is to establish a non-invasive breath test for early detection of EC cancer based on its unique profile of volatile organic compounds (VOCs). Our previous studies have reported higher concentrations of specific VOCs, including volatile fatty acids (butanoic-, pentanoic- and hexanoic acid), within the breath, gastric content and urine of EC cancer patients (1-4). We have also

established standardized and quality controlled protocols for breath sampling, transfer and storage that ensure accuracy and reproducibility of VOC analysis by mass spectrometry methods (5-9).

Infrastructure for research

Existing infrastructure at Virginia Mason Medical Center that will support the proposed study include: high volume center for the management of esophageal cancer; support from the Benaroya Research Institute at Virginia Mason including access to study coordinators, and; a track record for conducting high quality research in esophageal cancer.

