The proposed study will be conducted in collaboration with the volatile biomarker research group, based at St Mary's Hospital (Imperial College London). The primary focus of this group's research has been the non-invasive diagnosis of gastrointestinal cancer through the detection of VOCs within exhaled breath. They have previously established diagnostic models of gastroesophageal and colorectal cancers (8, 9, 15, 16). In a recent multicenter validation study they demonstrated a diagnostic performance of a breath test for gastroesophageal cancers based on five VOCs, with an area under the receiver operator characteristic curve of 0.85 and sensitivity and specificity of 80% and 81% respectively (15). Their previous work has alluded to importance of volatile fatty acids, aldehydes and phenols as tumor markers. In parallel to these clinical trials they have sought to investigate the mechanisms whereby VOCs are deregulated in cancer by undertaking carefully designed in-vitro and in-vivo studies. Specifically they have demonstrated an association between gastroesophageal cancer, its predominant associated bacterial species (E.coli, K. pneumoniae and S. anginosus) and VOCs production (unpublished data). Whilst these findings give support to the hypothesis that cancer has associated bacteria, no study has sought to directly compare the intestinal microbiome and exhaled VOC levels.

Critical knowledge gap: Previous studies have established an important link between deregulated VOC production and EC. These studies have all assessed exhaled VOCs at a single point in time using a cross-section study design. Longitudinal variation in exhaled and urinary VOCs, the contribution of the upper gastrointestinal microbiome and the effect of therapeutic intervention in EC cancer patients remain unknown. An understanding of this variation is critically important in establishing intra-subject variability and likely mechanisms of VOC production and release. Furthermore the expected decline in target VOCs following chemoradiotherapy and/or tumor resection would both verify the link between the tumor and aberrant VOCs production as well as offering an opportunity to utilize VOCs as a means to assess treatment response including the early detection of recurrence.

RESEARCH DESIGN AND METHODS

Study design: longitudinal cohort study

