Statistical analysis: Both univariate and multivariate data analysis techniques will be applied to identify breath and urinary VOCs with the best discriminating ability and to develop a multivariate discriminant analysis model. Appropriate univariate statistical techniques will be used to compare intra- and inter- individual variability in exhaled VOCs in response to therapeutic intervention. Associations between predominant bacterial species and VOCs will be determined through a univariate and multivariate data analysis techniques.

Using the data collected, several machine learning algorithms will be adapted, trained and evaluated for the purpose of diagnostic inference based on the breath sample chemical analysis. We will start with an exploratory analysis of the VOC concentration data, including Principal Component Analysis (PCA) and Multi-dimensional Scaling (MDS), to reduce the feature space and develop intuitions about the data. Next, Machine Learning Algorithms (MLA) such as Support Vector Machines (SVM) and k-Nearest Neighbors (kNN) will be trained and validated to reliably separate cancer from non-cancer cases. An Information Theory based MLA will also be developed. Cross-validation algorithms such as k -fold training will be used to rigorously assess the reliability of the learning algorithms. Models will then be compared through suitable accuracy scores and ROC curves will be produced to aid the selection of appropriate clinical diagnostic measure, which balances specificity against sensitivity.

Sample storage

Breath, urine and saliva samples will be stored in a -80°C freezer within the Benaroya Research Institute. Samples will be deidentified and only labeled using a unique study identifier composed of the patient's study ID and the date the sample was collected.

Data storage

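### For the diagnostic question the protocol describes only VOC selection and new model building, which neither validates the published five-VOC model nor tests markers named in advance

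*Protocol*

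**What the plan says.** The Protocol makes two claims that need something fixed beforehand, and lists model development separately.

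- Study Outcomes, primary outcome: "Confirmation of exhaled and urinary VOC biomarkers of EC cancer".
- Specific Aims, secondary aim i: "To validate the previously published model for a exhaled VOC breath test of EC cancer".
- Study Outcomes, secondary outcome ii: "Refine diagnostic model for the detection and monitoring of EC cancer through analysis of exhaled VOCs".

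The background supplies candidates that could be fixed. It describes a published breath test "based on five VOCs, with an area under the receiver operator characteristic curve of 0.85 and sensitivity and specificity of 80% and 81% respectively". It also reports raised concentrations of specific VOCs, "including volatile fatty acids (butanoic-, pentanoic- and hexanoic acid"). It does not name the five VOCs or give the model's coefficients or cut-off.

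The Statistical analysis section plans to "identify breath and urinary VOCs with the best discriminating ability and to develop a multivariate discriminant analysis model". It adds that "several machine learning algorithms will be adapted, trained and evaluated for the purpose of diagnostic inference", with PCA and multidimensional scaling to reduce the features, then support vector machines, k-nearest neighbours and an information-theory algorithm. These are assessed by k-fold cross-validation and compared by accuracy and ROC curves. The same section also plans univariate comparisons of within- and between-patient variability in response to treatment, and analyses of bacteria and VOCs.

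**The concern.** Validating a published model means applying it, with its own weights and cut-off, to patients who played no part in building it. Confirming a marker means testing one that was named before the data were seen. Choosing the VOCs that discriminate best in this cohort and fitting new weights to them does neither.

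The risk lies in reporting. If the stated analysis is followed and reported against the stated outcome and aim, VOCs and weights chosen from these data could be presented as confirmation and validation. How the published model behaves in these patients would go unexamined, even for the one property that this cohort can address.

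**Working it through.** **1. Aims against analysis.**

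| Stated goal | What it needs | Step in Statistical analysis |
|---|---|---|
| Validate published model (aim i) | Model locked and applied unchanged | None described |
| Confirm biomarkers (primary outcome) | VOCs and contrast named beforehand | None described; VOCs are chosen from the data |
| Refine diagnostic model (secondary outcome ii) | Selection, training, internal validation | Described at length |
| Longitudinal variation (primary aim) | Within-patient comparison | Described, but not tied to named VOCs |

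The only validation step is k-fold cross-validation, and it applies to the newly trained algorithms.

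**2. What a locked model could show.** The sample size is 50 curative tri-modality patients, set pragmatically, so there is no power calculation to reproduce. Suppose all 50 give a usable pre-treatment breath sample and the published sensitivity of 80% is observed exactly: 0.80 × 50 = 40 positives. The exact (Clopper-Pearson) 95% limits are:

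- lower: 2.5% quantile of Beta(40, 50 − 40 + 1) = Beta(40, 11), giving 0.663
- upper: 97.5% quantile of Beta(40 + 1, 50 − 40) = Beta(41, 10), giving 0.900

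The interval of about 66% to 90% is wide but informative. The published 80% refers to gastroesophageal cancers, whereas this cohort has esophageal and junctional cancers.

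**3. What it could not show.** Specificity and AUC both need people without the disease. Exclusion criterion ii removes them. The extra subjects described under Protection of Human Subjects are patients consented during diagnosis and staging of esophageal or junctional cancer who are then not recommended for tri-modality treatment; they are not planned non-cancer controls. The published 81% and 0.85 therefore have no counterpart here. Sensitivity alone is not validation, since a rule that calls everyone positive scores 100%.

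**4. Why a short named list still needs adjustment.** Assume 5% per test and independent tests with no true change. The chance of at least one false positive among m tests is 1 − 0.95^m:

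- m = 3 (the three acids): 14.3%
- m = 5 (the five model VOCs): 22.6%
- m = 8 (both lists, no overlap): 1 − 0.663 = 33.7%

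With m = 8, Holm compares the smallest p-value with 0.05/8 = 0.00625. The protocol gives no alpha, so 5% is an assumption. Testing in both breath and urine enlarges the family.

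**The case against.** **A separate analysis plan may supply the missing steps.** A marker list, a cut-off and a multiplicity rule are often left to such a plan, and one may exist. That stands as far as detail goes, so it cannot be said that validation or confirmation is impossible in this study. It does not remove the mismatch: the protocol itself states a diagnostic analysis, and that analysis answers a different question from its primary outcome and aim i.

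**A reader might infer that the plan does nothing but search and so cannot produce a negative result.** The documents do not support this. The Statistical analysis section includes a within-patient comparison across treatment, and the critical knowledge gap paragraph expects target VOCs to fall after chemoradiotherapy or resection. That expectation can fail. Cross-validation is also planned. In a simulation with pure-noise VOCs, 50 cases and an assumed 50 comparators, choosing the best five of 50, 100 or 200 gave mean apparent AUCs of 0.749, 0.779 and 0.801. With selection kept inside five folds, the means were 0.498, 0.509 and 0.504. The protocol does not say whether selection will be inside the folds. Because it also gives neither the number of VOCs nor any non-cancer group, these figures illustrate the mechanism only and do not predict this study's results.

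**The published model may not be applicable.** Breath VOCs are to be semi-quantified by GC-MS, and the documents do not give the model's measurement scale. This stands, so the fix must be conditional.

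**This is a pragmatic cohort leading to later work.** That also stands, and it lowers the severity. It is equally a reason to word the outcome and aim as what they are.

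**Conclusion.** The mismatch is real but limited. For the diagnostic question, the analysis as written does not validate the published five-VOC model and does not test markers named in advance. At best, a locked analysis of 50 pre-treatment samples gives a sensitivity estimate with a 95% interval of about 66% to 90% if 80% is observed; it cannot address specificity or AUC. This assumes that every patient gives a usable sample and that the GC-MS measurements can be placed on the model's scale. It also takes the protocol as the stated analysis, with no separate plan at hand.

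This should be fixed before the data are analysed. It affects what may be claimed, not how patients are recruited or sampled.

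**What to change.** 1. **Published model.** In Statistical analysis, before any re-selection, apply the published model with its own coefficients and cut-off, unchanged, to the pre-treatment breath samples, provided the GC-MS semi-quantification is comparable with the model's measurements. Report the proportion called positive with an exact 95% CI. Reword aim i as a check of sensitivity only, and state that specificity and AUC cannot be assessed without non-cancer subjects. If the model cannot be applied, reword the aim as exploratory.
2. **Confirmation.** Limit the word to VOCs listed by name in the protocol: the five in the published model and the three fatty acids in the background. Test within-patient change from pre-treatment to one named later time point, in the expected direction of decline, with Holm adjustment across the list, and state whether the family covers breath, urine or both. Such a test supports a link to the tumor or its treatment, not diagnostic discrimination, and the outcome should say so.
3. **Everything else.** Label other VOC selection and all newly trained models as exploratory development under secondary outcome ii.

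The cost is wording in two sections, a check of measurement comparability, and analyses of samples already scheduled. No added visits or patients are needed. The price is a narrower headline claim.

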Sample size: 50 curative tri-modality patients. Study sample size has been determined pragmatically based on estimated patient recruitment during the course of 1 year in a high volume center for the management of EC

Human subjects: patients undergoing potentially curative therapy for EC cancer at Virginia Mason Medical Center who meet the eligibility criteria will be invited to participate in this study.

Inclusion criteria: patients with the following characteristics will be eligible for inclusion in this study:

- i. aged 18-90 years
- ii. newly diagnosed, treatment naïve patients with esophageal and/or gastroesophageal junctional cancer
- iii. planning to undergo curative treatment, including neoadjuvant chemoradiotherapy and surgical resection

Exclusion criteria: patients with the following characteristics will not be eligible for inclusion in this study:

- i. pregnant females
- ii. without malignant esophageal disease
- iii. malignancy at a secondary site other than the esophagus
- iv. patients undergoing palliative treatment for esophageal cancer
- v. patients not receiving neoadjuvant chemoradiotherapy and surgical resection for esophageal cancer
- vi. inability or unwillingness to provide written informed consent

Study time points: subjects will be asked to provide exhaled breath, urine and saliva samples at the following time points during their routine care:

- i. Before commencing treatment for esophageal cancer*
- ii. Following conclusion of neoadjuvant therapy (at the time of a routine outpatient appointment or on the day of surgery)
- iii. Following surgical resection (after the removal of the nasogastric tube, during the inpatient hospital stay)
- iv. At the time of routine postoperative follow-up at VM (between six months to one-year following surgery)

Subjects will also be asked to complete an engagement questionnaire at one of the study timepoints. See "Subject Engagement" section of the protocol.

*Where feasible at the time of initial breath sampling subjects will be asked to provide breath samples on two separate routine clinical appointments (often on consecutive days) in order to assess short-term temporal variation in exhaled VOC levels. At the

time of their initial assessment it is common for patients to have routine clinical appointments on consecutive days.

Any data that are not able to be collected with reasonable efforts will not be considered protocol deviations.

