Virginia Mason Medical Center subject data will be stored in a pseudonymized form within Microsoft Excel. Data will be stored on a password protected institutional (Virginia Mason Medical) computer. Any paper records, including patient consent forms, will be stored in locked filing cabinet within the department of Thoracic Surgery Virginia Mason Medical Center as well as in the Clinical Research Program offices at Benaroya Research Institute. Access to the data will be limited to the principal investigator, nominated members of the research team and any regulatory or institutional compliance team member in case of review or audit only. Any data from samples shared with Imperial College London (UK) will be in a linked anonymized form.

Subject engagement: Subjects who are recruited to this study will be asked to complete a short survey, ideally at the first study time point (but acceptable to be collected at any study time point), designed to assess their understanding and opinions regarding breath testing.

PROTECTION OF HUMAN SUBJECTS

Human Subject involvement and characteristics

Human subjects will be enrolled into this study. The purpose of recruiting human subjects is to determine the influence of EC and neoadjuvant therapy on VOC biomarkers and the upper gastrointestinal microbiome. Recruitment of human subjects is critical to achieving the intended outcomes of this study.

Patients with newly diagnosed esophageal and/or gastroesophageal junctional adenocarcinoma will be recruited from Virginia Mason Medical Center (n=50). Patients will be asked to donate an exhaled breath, urine and saliva sample at four study time points. With the exception of a subject engagement questionnaire (completed at the time of the first study visit) all other data that are utilized as part of this study originates from patients' routine clinical care and their electronic medical record.

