Patients who appear to meet study eligibility may sign consent for this study during the diagnosis and staging phase of esophageal and/or gastroesophageal junctional adenocarcinoma. Initial samples will be collected for these subjects after consent is obtained. Upon completion of diagnosis and staging, it is possible that the subject may not be recommended for curative tri-modality treatment (surgical resection and chemoradiation therapy). Although these subjects are not the focal population for this study, their samples at the applicable study time points are valuable for comparison purposes. As such, these subjects will continue to have samples captured at the protocol defined study time points whenever possible, but any samples not collected (generally due to the subject not returning to VM within the appropriate timeframe) will not be considered a protocol deviation. These subjects will not count toward the goal of 50 enrolled curative tri-modality subjects. Their data will be comparative only.

We do not plan to enroll vulnerable subject groups (children, persons with mental disability, prisoners) where ability to give voluntary informed consent may be questioned or compromised.

Collaborating sites

This work will be conducted as part of a collaboration between Virginia Mason Medical Center (Seattle, USA) and Imperial College London (London, UK).

Sources of Materials

Patients will be required to provide written informed consent prior to enrollment in this study. Participants will be provided with an approved informed consent form and will receive careful explanation by the investigator or approved delegate of the study team consisting of what is involved by taking part in the study, including potential risks and benefits.

- i. Patient demographics and meta-data will be recorded for all patients (please see data collection section above). There is very little risk of breach of confidentiality.
- ii. Breath samples: breath sampling is entirely non-invasive and poses negligible risk of harm to patients. Patients will be asked to provide a breath sample by blowing directly into a disposable (single use) sample bag. The sample is then transferred and stored within a Thermal Desorption (TD) tube. Samples will be analyzed at Imperial College London. Breath samples are destroyed during the analysis process.

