- iii. Urine samples: urine sampling is entirely non-invasive and poses negligible risk of harm to patients. Patients will be asked to provide a urine sample (10ml) by urinating into a sample pot that they will be provided with. The sample will be analyzed at Imperial College London. Urine samples will be destroyed following the analysis process.
- iv. Saliva samples: saliva sampling is entirely non-invasive and poses negligible risk of harm to patients. Patients will be asked to provide a saliva sample (1-3ml) by expectorating into a sample pot that they will be provided with. The sample will be analyzed at Imperial College London. Saliva samples will be destroyed following the analysis process.

Potential Risks

Risks and benefits

The principal risks of this study relate to the preservation of patient confidentiality in a multicenter study.

All study related documents and patient information for subjects enrolled in this study will be stored securely within a password protected networked computer at Virginia Mason. Hard copies of consent forms and paper questionnaires will be stored in a locked filing cabinet within the Benaroya Research Institute at Virginia Mason. The same standards regarding data and sample storage are practiced at Imperial College London.

Patients recruited to this study are being considered for curative treatment of esophageal cancer involving chemoradiotherapy and surgery. During the course of their treatment patients will be regularly required to fast and undergo invasive investigations and treatments. The risk of additional non-invasive interventions including breath, urine and saliva sampling are therefore considered to be negligible. Breath, urine and saliva sampling will be performed at the time of a routine clinical visit to avoid patients having to make additional visits to the hospital.

It is intended that the current study should have minimal impact on patient's routine clinical care. No extra financial costs will be passed to patients or their insurance provider.

Whilst no direct benefit is intended for individuals who agree to take part in this study, some patients may receive altruistic reward through participation in medical research that seeks to help other patients in the future.

Benefit is intended for future patients by establishing a greater understanding of methods of assessing and monitoring nutritional status in the setting of EC and surgery.

Adequacy of Protection Against Risks

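### The protocol plans cancer versus non-cancer classifiers and a specificity-based choice of test, but it enrols no one without cancer and names no control data

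*Protocol*

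**What the plan says.** The Statistical analysis section states the data source, the target and the output of the classifiers. The source is this study: "Using the data collected, several machine learning algorithms will be adapted, trained and evaluated for the purpose of diagnostic inference". The target is two classes: the algorithms "will be trained and validated to reliably separate cancer from non-cancer cases". The output is a set of accuracy scores and ROC curves, the latter "to aid the selection of appropriate clinical diagnostic measure, which balances specificity against sensitivity".

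The cohort is defined elsewhere in the Protocol.

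- Inclusion criterion ii admits newly diagnosed, untreated "patients with esophageal and/or gastroesophageal junctional cancer".
- Exclusion criterion ii removes those "without malignant esophageal disease".
- The sample size is 50 tri-modality patients. The Human Subject involvement section gives the same 50 and describes them as newly diagnosed cancer patients.
- The Risks and benefits section describes the cohort in the same way: "Patients recruited to this study are being considered for curative treatment of esophageal cancer involving chemoradiotherapy and surgery".
- The only comparison group consists of people who consent during diagnosis and staging, for whom "it is possible that the subject may not be recommended for curative tri-modality treatment". They have no planned number, do not count towards the 50, and serve for comparison only.

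Two stated objectives draw on the classifier work: secondary aim i (validating the published breath-test model) and secondary outcome ii (refining a model for detection and monitoring).

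**The concern.** A classifier that separates two classes needs data from both. The analysis section ties training and validation to this study's own data, and the eligibility criteria remove one of the two classes. The conflict lies between two parts of the Protocol, so it is not a detail left for a statistical analysis plan. Such a plan can set tuning, validation folds and accuracy measures, but it cannot supply a class of subjects that eligibility excludes and for which no other source is named.

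At stake is what the study may claim about detection. This paragraph is the most detailed part of the Protocol's only analysis section. If it stays, a contrast that can be run within the cohort (before versus after treatment, responder versus non-responder, recurrence versus none) could be reported as diagnostic accuracy. None of these measures how often the test is wrongly positive in people who do not have cancer.

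**Working it through.** **Can the stated quantities be estimated?** Inputs: 50 cancer patients (Sample size); 0 planned non-cancer subjects (inclusion ii and exclusion ii); four sampling time points (Study time points).

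1. Scheduled breath sample sets: 50 × 4 = 200, plus optional repeat baseline samples. Sets from people enrolled as cancer-free: 0.
2. Specificity = TN / (TN + FP). With no non-cancer subjects this is 0/0, undefined.
3. Empirical AUC = concordant pairs / (n cancer × n non-cancer). The denominator is 50 × 0 = 0, undefined.
4. A cut-off that trades specificity against sensitivity needs item 2, so it cannot be chosen either.

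The sample size of 50 was set pragmatically from expected recruitment in one year. It has no power or precision target, so there is no planned figure to reproduce.

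**Does any other source in the Protocol supply the missing class?**

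| Possible source | What the Protocol says | Result |
|---|---|---|
| Patients not recommended for tri-modality treatment | Set apart by treatment recommendation, during work-up for adenocarcinoma | Not defined as cancer-free; anyone found cancer-free would meet exclusion ii |
| Samples after resection (time points iii and iv) | 50 × 2 = 100 of the 200 sets; never labelled non-cancer | Same patients, after chemoradiotherapy, surgery and altered anatomy; aim iv anticipates recurrence |
| Collaborators' earlier studies | Cited as background under Infrastructure for research | Not named as input data |
| Institutional database IRB18-076 | Source of metadata and place of long-term storage | Not named as a control source |

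**What remains estimable.** Sensitivity of a fixed model needs cancer patients only. Assume the 80% that the Protocol quotes for the published model, and an evaluable baseline sample from all 50: 40/50, with a Clopper-Pearson 95% CI of 0.663 to 0.900.

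**Precision if the classifiers are redirected to treatment response.** The AUC and class sizes here are assumptions; they describe the repair and are not evidence of the defect. Hanley-McNeil: SE² = [A(1−A) + (n1−1)(q1−A²) + (n0−1)(q2−A²)] / (n1·n0), with q1 = A/(2−A) and q2 = 2A²/(1+A). For A = 0.75, q1 = 0.600, q2 = 0.643 and A² = 0.5625.

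- 25 responders, 25 non-responders: SE² = (0.1875 + 0.900 + 1.929)/625, SE = 0.0695, 95% CI 0.614 to 0.886.
- 10 responders, 40 non-responders: SE² = (0.1875 + 0.3375 + 3.134)/400, SE = 0.0956, 95% CI 0.563 to 0.937.
- 40 responders, 10 non-responders: SE = 0.0770, 95% CI 0.599 to 0.901.

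**The case against.** The strongest reply is that an ROC curve can be computed. The Protocol speaks of non-cancer cases, not cancer-free people, half of the scheduled sample sets follow tumor removal, and the background expects the target compounds to fall after treatment. This is correct as far as it goes: a before-versus-after curve is computable. But the Protocol nowhere labels the later samples non-cancer. The contrast is paired within patients and confounded with treatment, and possible recurrence blurs the label. It would describe change under therapy, not specificity for detection.

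Second, external controls are unnamed but not ruled out. The collaborating laboratory built the earlier models, and outcome ii speaks of refining a model. This softens the point without removing it, because the text ties the classifiers to the data collected here and names no other source.

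Third, the harm is limited: part of one secondary aim and part of one secondary outcome in a non-interventional cohort, with no effect on safety or sampling. That is a fair account of the scope for the aims. It is slightly too generous for the stated primary outcome, confirmation of exhaled and urinary biomarkers of the cancer, which is also affected so far as confirmation is taken to need a non-cancer comparison.

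Finally, the response intervals above rest on assumed values. That is so, and the finding does not depend on them.

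**Conclusion.** The concern holds. The detection analysis cannot be run on the cohort as described: 50 cancer patients, 0 planned non-cancer subjects, and no named control set. Specificity, the cancer versus non-cancer AUC and the diagnostic cut-off are undefined, not merely imprecise. This follows from the Protocol's text and needs no assumption.

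The affected parts are the specificity and AUC half of secondary aim i and the detection element of secondary outcome ii. The longitudinal primary aim, aims iii and iv (including any ROC curves for response or recurrence) and the sensitivity of a fixed published model are unaffected. The sensitivity interval of 66% to 90% assumes 80% detected and all 50 baselines evaluable. The assumed response scenarios give intervals from about 0.61 to 0.89 at best to 0.56 to 0.94 at worst, so response classifiers from this cohort would be exploratory. The conflict must be fixed before the detection analysis is run or reported.

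**What to change.** Choose one of two routes.

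**(a) Limit the claim to what the cohort supports.**

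1. In Statistical analysis, remove the cancer versus non-cancer classification and the ROC and specificity selection for detection.
2. Direct the classifiers to treatment response (aim iii) and, where there are enough events, recurrence (aim iv). Keep all samples of a patient in the same validation fold and label the results exploratory.
3. Report differences between pre- and post-treatment samples as descriptive within-patient change, not as diagnostic accuracy.
4. Restate secondary aim i as applying the published model unchanged to pre-treatment samples and reporting sensitivity with an exact 95% CI, provided the model transfers to this semi-quantitative GC-MS assay. If it does not, report only within-patient change in score.
5. Limit secondary outcome ii to monitoring, and state what confirmation means in the primary outcome without a non-cancer group.

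Cost: an amendment to an IRB-approved protocol and a check of assay transfer. No new patients or procedures are needed. The diagnostic claim becomes narrower.

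**(b) Keep the detection claim.** Name in the Protocol an existing non-cancer data set, its size, and the evidence that its breath sampling and assay are comparable with this study's. Cost: access to those data and documentation of comparability.
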